## 1. SPECIFIC AIMS

We propose a large pragmatic clinical trial to inform patient choice and balance risk tolerances of individuals who face decisions about different drugs and strategies for deep vein thrombosis (DVT) and pulmonary embolism (PE) prevention after total hip (THA) and knee (TKA) replacement. Indeed, clinical equipoise exists to ethically support such a randomized trial that has great potential to change current practice. We have selected the three prophylaxis methods that represent current orthopaedic practice in North America and collectively account for more than 80% of all hip and knee replacements; a) enteric coated aspirin (regimen with lowest bleeding risk; clinical PE and all-cause mortality rates comparable to more intensive anticoagulants), b) low intensity (INR 1.5-2) warfarin (time honored and one of the most common North American regimens; low bleeding risk [1-2%]), and c) rivaroxaban, a new oral direct Factor Xa inhibitor (regimen with lowest PE and DVT rate but higher bleeding risk [3-5%]). Prophylaxis will continue for 30 days, in accordance with clinical guidelines, and pneumatic compression will be utilized in hospital in conjunction with aspirin, warfarin, or rivaroxaban according to local practice. Each regimen is commonly used in contemporary practice, supported by observational and clinical trial data, and endorsed by the American College of Chest Physicians (ACCP) and American Academy of Orthopaedic Surgeons (AAOS) guidelines.

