## 2. BACKGROUND AND SIGNIFICANCE

### 2.1. Background

Osteoarthritis is the most common form of arthritis and involvement of the hip and knee is a leading cause of long-term disability and time missed from work. The societal burden of this condition is substantial. Elective total joint replacement of the hip (THA) and knee (TKA) comprise the most commonly performed procedures in the US, totaling nearly 1 million annually. Moreover, THA and TKA are increasing in number with the aging of the baby boomer generation and collectively stand out as the single largest expenditure for Medicare. Readmission to the hospital within 90 days of operation occurs after 10-15% of elective hip and knee replacements and venous thromboembolism (VTE; blood clots in the veins), specifically pulmonary embolism (PE; blood clots in the lung), is one of the most common causes. Despite advances in surgical and perioperative care, fatal PE occurs in 0.1 to 0.5% of patients and is responsible for more than 1,000 patient deaths each year following these operations. Appropriately, considerable effort has been directed at identifying the best method to prevent venous thromboembolism in these patients. However, use of potent anticoagulants soon after orthopaedic operations to reduce the risk of blood clots must be tempered by consideration of the bleeding risk implicit in these procedures. Orthopaedic surgeons typically opt for one of three main regimens for preventing these clots, and guideline recommendations for use of blood thinners have historically been conflicted. The ideal prophylaxis will represent a balance between the risk of fatal pulmonary embolism and the morbidity of bleeding resulting in a hematoma (old blood accumulating in the wound) or secondary infection related to anticoagulant use. Such a critical decision requires clear and definitive evidence about the potential benefits and harms of blood thinners used to prevent clots after operation, as well as knowledge of individual patient preferences about these tradeoffs and risks.

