reoperation, and infection more than they fear a 1 in 1,000 risk of death from PE after joint replacement. Similarly, an IRB-approved questionnaire (Appendix C) was utilized to assess prospective and past joint replacement patients' preferences regarding the tradeoff of PE prevention and bleeding for several months prior to submission of this application; this information validated prior assumptions and guided design of the proposed trial. Finally, a subset of patients enrolled in the trial will participate in a conjoint analysis exercise to explore risk tolerance for specific outcomes: death from PE; symptomatic PE/DVT; bleeding leading to delayed wound healing, pain, and stiffness; reoperation to drain a collection of blood from the wound; and infection necessitating removal of the implant. Patients will review and rate orthogonal sets of alternatives with varying probabilities over the plausible range of each outcome to assess the value proposition of relative likelihood of the different adverse events. Any apparent inequality in seriousness of paired outcomes will be balanced by relative likelihood of each; fatal PE is a 1-2 in 1,000 event compared to the aggregate of bleeding and reoperation, which is a 1-5 in 100 event. As seen in both the Dartmouth community survey and the pre-application patient questionnaire, it is anticipated that this information will reveal an underappreciated risk aversion of patients for bleeding events because they are less common than VTE/PE and negatively impact recovery and eventual function after operation. We believe that physicians and payers disproportionately value in-hospital VTE and adverse safety events because they do not witness the more subtle compromise in function and patient well-being that does not result in death or readmission. These outcomes are typically more insidious in their presentation, occur after hospital discharge, and are more apparent to the patient and surgeon than to guideline authors. This information will inform non-patient stakeholders about what patients perceive as the greatest threat to their well-being; potentially fatal thromboembolism or bleeding that can result from aggressive perioperative anticoagulation efforts to prevent VTE.

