#### d) Randomization

Randomization of consented patients occurs after the surgeon confirms eligibility and up until the day before the originally scheduled surgery date. If a patient's surgery is postponed, or cancelled and ultimately rescheduled, the patient will keep the original randomization assignment. The ability to randomize a patient will be available via the web-based randomization system once consent has been signed and all baseline instruments have been entered into the database. Study group assignments will be shared with the surgeon at the time of randomization, and with the patient on the day of operation unless necessary to provide third party insurance coverage for prescribed medical care.

Patients will be assigned to treatment groups using a web-based randomization system. A permuted block randomization scheme will be utilized to ensure equal assignment of patients to each drug study group at each participating site, taking into consideration the noted criteria for stratified randomization. In the absence of any randomization stratification requirements, patients meeting all eligibility criteria without any randomization exclusions will be assigned to one of two groups; a concealed centralized randomization schedule will provide assignment to one of two prophylaxis regimens (aspirin or rivaroxaban) in randomly varying block sizes developed separately for each clinical site and stratified according to type of surgery (hip or knee replacement). Prophylaxis will continue for 30 days, in accordance with clinical guidelines, and pneumatic compression devices will be utilized in hospital in conjunction with both of the treatment groups according to local practice. The two groups are as follows:

- 1) Enteric coated aspirin (regimen with lowest bleeding risk; clinical PE and all-cause mortality rates comparable to more intensive anticoagulants); and
- 2) Rivaroxaban, an oral direct Factor Xa inhibitor (regimen with lowest PE and DVT rate but higher bleeding risk [3-5%]).

A contraindication to one of the two study prophylaxis regimens for venous thromboembolism is exclusionary. The contraindications to aspirin are:

- 1) Patients with a known aspirin allergy;
- 2) Patients with a personal history of PE or DVT;

- 3) Patients with a known condition of thrombophilia proven by diagnostic testing; e.g. Factor V Leiden;
- 4) Patients with a cancer diagnosis who are under active treatment.

The contraindications to rivaroxaban are:

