## **5.0 Power and Precision**

**5.1 Sample Size.** We expect to recruit 20,000 participants. Conservatively assuming 10% of them will not be evaluable, we expect to have data on 18,000 patients. It is estimated that 5% of the patients will be ineligible for aspirin,

2% will be ineligible for rivaroxaban and 1% will be ineligible for Warfarin. It is also estimated (based on the first 6 months of data) that 2.5% of those assigned to aspirin will not be treated with aspirin, 6.4% of those assigned to warfarin will not be treated with warfarin, and 13.6% of those assigned to rivaroxaban will not be treated with rivaroxaban. These patients will be excluded from the primary analysis. Therefore, with a total sample of approximately 20,000, we project that there will be 7239, 7223, and 5389 patients assigned to and treated with aspirin, Rivaroxaban, and Warfarin groups, respectively. We expect to have six-month outcome data on the vast majority of the patients, so we based our precision and power calculations on a binary outcome.

**5.2 Precision of Estimates.** The primary endpoint is a composite consisting of the occurrence of death from any cause and clinically evident PE or DVT. For an observed endpoint that occurs 1.1% of the time, considering the cross-over rates and conservatively assuming that 10% of those randomized will not have surgery or will be lost to follow-up, the margin of error of our estimates of risk will be 0.27%, 0.30%, and 0.35% for aspirin, rivaroxaban, and warfarin. Clinically significant bleeding is expected to occur in 0.5-1% of patients on aspirin, 4-5% of patients on rivaroxaban, and 1-2% of patients on warfarin. Given those percentages, the margin of error for estimates of bleeding risk will be 0.22%, 0.61%, and 0.41%, respectively.

**5.3 Power to confirm non-inferiority.** The adoption of a non-inferiority methodology for this trial was predicated on establishing the non-inferiority of aspirin, as compared to either warfarin or rivaroxaban, in preventing death and thromboembolic disease with the assumption that aspirin would very likely result in fewer bleeding complications than either of these two agents. The statistical test of non-inferiority will be based on only those who were medically or logistically eligible for randomization to either of the two groups being compared. Table 1 shows the power to detect non-inferiority for the comparison of aspirin to warfarin with no additional patients randomized to warfarin.

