#### 4.1.3. Potential Risks

Risks to human subjects in this trial include any and all of those typically experienced in the course of “standard of care” treatment and prophylaxis for venous thromboembolism after total hip or knee replacement. There are no experimental drugs or treatment regimens involved in this trial, and so there are no risks associated with any experimental interventions. Likewise, there are no other special risks that are unique to this trial. There are risks associated with randomization since patients will be assigned to a treatment group by chance. One treatment group may prove to be more or less effective or to have more or fewer side effects than the other study treatments or other available treatments. However, each of the three regimens in this trial is commonly used in “standard of care” practice following hip and knee replacement surgery and each has been approved by the FDA and expert guideline groups for use in this manner to prevent venous thromboembolism.

Each of the anticoagulants carries a risk of bleeding, reoperation to evacuate a hematoma from the incision, and secondary infection of the hematoma. Aspirin may cause gastritis and intestinal bleeding may result, or patients may develop an allergy to aspirin that interferes with breathing. Warfarin may accumulate in patients who have liver disease or result in an idiosyncratic reaction with elevation of the INR and may require reversal. Rivaroxaban may accumulate in patients who have kidney disease and may require reversal. Pneumatic compression stockings or foot pumps may be annoying or uncomfortable while wearing them in the hospital. The estimated likelihood of the risks of pulmonary embolism and re-operation for bleeding are as follows:

Medication	Reoperation for Bleeding	Pulmonary Embolism
Aspirin	1 in 500 (0.2%)	1 in 50 (2.0%)
Warfarin	1 in 100 (1.0%)	1 in 100 (1.0%)
Rivaroxaban	1 in 20 (5.0%)	1 in 200 (0.5%)

Serious adverse events (SAE) will be defined as any death or unplanned readmission to the hospital, reoperation or other procedure related to the index operated joint, transfusion, aspiration of the operated joint, or any other event that may be attributed to use of one of the anticoagulant medications central to the clinical trial. SAEs will be considered by the DSMB in their regular reviews and reported to the IRB as appropriate and determined by the DSMB and executive oversight group.

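### Reoperation for bleeding on rivaroxaban (5.0%) equals or exceeds the 4-5% given for all clinically significant bleeding on that drug, and the stated bleeding margin does not follow from the projected counts

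*Protocol*

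**What the plan says.** The protocol gives a bleeding figure for rivaroxaban in four places.

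- **Section 1, Specific Aims:** "rivaroxaban, a new oral direct Factor Xa inhibitor (regimen with lowest PE and DVT rate but higher bleeding risk [3-5" percent. The kind of bleeding is not stated.
- **Section 3.1.2 d, Randomization:** "Rivaroxaban, an oral direct Factor Xa inhibitor (regimen with lowest PE and DVT rate but higher bleeding risk [3-5" percent, again undefined.
- **Section 3.1.3, item 5.2, Precision of Estimates:** "Clinically significant bleeding is expected to occur in 0.5-1% of patients on aspirin, 4-5% of patients on rivaroxaban, and 1-2% of patients on warfarin". The margins of error given for these are 0.22, 0.61 and 0.41 percentage points for aspirin, rivaroxaban and warfarin.
- **Section 4.1.3, Potential Risks:** a table by drug, introduced with "The estimated likelihood of the risks of pulmonary embolism and re-operation for bleeding are as follows". Its reoperation column reads 0.2% for aspirin, 1.0% for warfarin and 5.0% (1 in 20) for rivaroxaban.

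Section 3.1.2 g, Outcome Determination, lists bleeding that leads to reoperation as one of several ways in which a bleed counts as major. The others include fatal bleeds, bleeds in a critical organ or space, and overt remote-site bleeds with a haemoglobin fall, transfusion or longer stay. Wound drainage beyond five days is a separate, non-major category.

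**The concern.** If reoperation for bleeding is one component of major bleeding, its rate cannot exceed the rate of all clinically significant bleeding in the same patients. It should normally lie well below it, because the definition admits other kinds of bleed. On rivaroxaban the component is at or above the total over the whole stated range.

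Two things depend on these numbers. The table in section 4.1.3 is the protocol's only by-drug statement of reoperation and PE risk, and it stands in the human-subjects section. The rate in item 5.2 is the planning basis for the only precision stated for the bleeding comparison in Primary Aim 2. Aspirin against rivaroxaban is also the only pair still being randomized, so rivaroxaban is the row where an unreconciled figure matters most.

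**Working it through.** **1. The table's own conversions.** 1/500 = 0.2%, 1/100 = 1.0%, 1/20 = 5.0%. The stated odds and percentages agree, so the 5.0% is not a conversion slip within the table.

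**2. Part over whole.** Share reoperated = reoperation for bleeding (section 4.1.3) / clinically significant bleeding (item 5.2).

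| Drug | Reoperation | All clinically significant bleeding | Share |
|---|---|---|---|
| Aspirin | 0.2% | 0.5-1% | 0.2/1 to 0.2/0.5 = 20-40% |
| Warfarin | 1.0% | 1-2% | 1/2 to 1/1 = 50-100% |
| Rivaroxaban | 5.0% | 4-5% | 5/5 to 5/4 = 100-125% |

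Against the undefined 3% lower end in sections 1 and 3.1.2 d the share would be 5/3 = 167%. Item 5.2 is the firmer comparator because it says what kind of bleeding it means. In counts, on the 7,223 rivaroxaban patients projected in item 5.1, the table implies 0.05 × 7,223 = 361 reoperations for bleeding. Item 5.2 implies 0.04 × 7,223 = 289 to 0.05 × 7,223 = 361 clinically significant bleeds of every kind.

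**3. The stated margin for rivaroxaban bleeding.** Margin = 1.96 × √(p(1−p)/n). Solving for n at 0.61 points:

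- p = 4.5%: n = 1.96² × 0.045 × 0.955 / 0.0061² = 4,437
- p = 5%: n = 1.96² × 0.05 × 0.95 / 0.0061² = 4,904

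The 0.30-point margin that item 5.2 gives for the primary endpoint on rivaroxaban points to a similar size: 1.96² × 0.011 × 0.989 / 0.0030² = 4,644. Both are well below the projected count.

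**4. The margin from the projected counts.** Item 5.1 projects 7,223 patients assigned to and treated with rivaroxaban, and item 5.2 allows 10% for no surgery or loss to follow-up: 7,223 × 0.90 = 6,501. It is not certain that 7,223 is already net of crossover. The matching warfarin figure, 5,389, is the number that Table 1 reports as randomized. So a second case also removes the 13.6% crossover: 6,501 × 0.864 = about 5,620.

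| n | p = 4.5% | p = 5% |
|---|---|---|
| 6,501 | 0.50 points | 0.53 points |
| 5,620 | 0.54 points | 0.57 points |

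Neither case reproduces 0.61.

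**5. Does this reach the non-inferiority power?** Table 1 (aspirin against warfarin) is reproduced with 1.1% in both arms, n = 3,962 and 3,319, a margin of 0.69 points and one-sided alpha 0.025: power 80.3%, confidence interval width 0.96 points, both as stated. No bleeding figure enters.

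**The case against.** The strongest defence is that the figures can coexist. The table gives rounded odds labelled as estimates, and 1 in 20 is the top of both bleeding ranges. The ranges in sections 1 and 3.1.2 d are also not defined as all bleeding, so the 167% should not carry the argument. Both remarks are fair. They reduce the finding from an impossibility to a figure that works only at one endpoint, and there only if no patient has a clinically significant bleed without reoperation. Rounding does not rescue it. Had 1 in 20 been rounded up from, say, 1 in 25 (4.0%, an assumed value), the share would still be 4/5 to 4/4 = 80-100%.

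A reader might infer more than the protocol supports, in four ways.

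- **That the fatal-PE figures conflict.** Section 2.1 says "fatal PE occurs in 0.1 to 0.5% of patients" and section 3 says "fatal PE is a 1-2 in 1,000 event compared to the aggregate of bleeding and reoperation, which is a 1-5 in 100 event". The second PE range (0.1-0.2%) lies inside the first, so one true rate can satisfy both.
- **That the conjoint exercise is capped at these values and tilts answers toward bleeding aversion.** Section 3 says that probabilities will vary over each outcome's plausible range, and it shows no attribute levels. The quoted sentence only explains how outcomes of unequal seriousness are paired.
- **That participants are told of a 25-fold gap (5.0/0.2).** The consent text is not available, and section 4.2.1 says only that risks will be described. Setting this against the 4- to 10-fold gap in bleeding (4/1 to 5/0.5) also compares two different outcomes.
- **That true total bleeding must be much higher, for example 8-10%, with a wider margin.** No such rate is in the protocol. The conflict could equally be resolved by a lower reoperation figure.

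**Conclusion.** The inconsistency is real and narrow. On rivaroxaban, reoperation for bleeding is 100-125% of all clinically significant bleeding as planned in item 5.2, while aspirin and warfarin stay at or below 100%. The protocol does not show which figure is at fault. Separately, the 0.61-point margin corresponds to about 4,400-4,900 patients. The projected counts give about 0.50-0.53 points, or 0.54-0.57 with crossover removed, so at 4.5-5% the stated precision errs on the cautious side.

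This rests on three assumptions: that clinically significant bleeding in item 5.2 includes at least the major bleeding defined in section 3.1.2 g; that the table and item 5.2 refer to the same patients and a similar period; and that the margins are ordinary 95% normal-approximation half-widths. The primary hypothesis, the 0.69-point margin and the Table 1 power do not change. The figures should be corrected, but the design is not in question.

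**What to change.** Reconcile sections 1, 3.1.2 d, 4.1.3 and item 5.2 into one sourced table by drug. It should give all clinically significant bleeding (with its definition tied to section 3.1.2 g) and reoperation for bleeding, and the second must not exceed the first. The sponsor should settle the values from its sources; this review does not presume which figure is right. Any consent text drawn from the section 4.1.3 table should be checked against the result.

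Then restate the rivaroxaban bleeding margin in item 5.2 from the reconciled rate. Give the number of patients behind it, and say whether 7,223 is before or after crossover.

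The cost is protocol wording and one recalculated margin, plus a consent amendment only if the consent form carries the affected figures. No change to the sample size or the analysis follows.

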### 1.1. Primary Aims

The Primary Specific Aims of the research are:

1) To compare the frequency of the aggregate primary clinical endpoints of important venous thromboembolism (clinical PE and DVT leading to hospital readmission) and all-cause mortality (aggregate indicator of fatal events, including both PE and major hemorrhage related to anticoagulant use) among three different venous thromboembolism (VTE) prophylaxis regimens. An audit of all hospital readmissions within 6 months of operation will be accomplished by routine postoperative follow-up through a mechanism of central telephone surveillance of patient-reported outcome events that is augmented by on-site research coordinator follow-up and validation of suspected endpoint events and adverse outcomes.

2) To compare the frequency and nature of bleeding complications (major, clinically important, and wound-related) leading to wound drainage, reoperation, deep infection, or myocardial infarction among three different VTE prophylaxis regimens. Bleeding complications are defined below and will be weighted relative to other events by the Patient Advisory Board.

3) To compare the groups with respect to patient-reported outcomes in order to assess their impact on specific function of the replaced joint as well as general patient well-being. Validated functional outcome tools will be compared among patients with and without primary endpoint events, as well as with historical baseline data warehoused in the FORCE registry, a national AHRQ funded joint replacement outcomes database. Study site overlap with the FORCE registry is planned.

### 1.2. Secondary Aims

The Secondary Aims include:

a) Analysis of the contribution of “standard of care” methods of anesthesia on clinical effectiveness of three different prophylaxis regimens. Stratification and subgroup analysis between patients with general compared with regional neuraxial (spinal/epidural) anesthesia will assess contribution of anesthesia to efficacy of VTE prophylaxis.

b) Analysis of the relative frequency of thromboembolic events and bleeding complications between hip and knee replacement patients with each of the three regimens. Evidence suggests etiology of venous thromboembolic disease (VTED) differs between THA and TKA and each may warrant a distinctive prophylaxis regimen based on likely outcomes.

c) To compare patient preferences and risk tolerances (represented by the Patient Advisory Board) with those of physician stakeholders (Steering Committee minus patient members) to contrast two potentially disparate perspectives. Understanding discordant patient-physician goals and risk tolerances will best serve choice of optimal VTE prophylaxis.

The current worldwide COVID-19 pandemic has led to the cancellation of many scheduled orthopaedic surgical procedures, including THA and TKA, secondary to shortages of personal protective equipment (PPE) as well as an effort to limit virus exposure of patients and hospital staff. This new health care reality, combined with social distancing and stay at home orders, have resulted in a historic rise in unemployment, affecting insurance coverage and the ability of patients to absorb related co-pays for medical care. Collectively these events will have profound and lasting

impacts on the delivery of care. Total joint replacement will likely see a change in volume after this pandemic due to the discretionary nature of this procedure which is impacted by both patient and health care system related factors.

Increased susceptibility of older patients to the virus and Covid-related propensity for venous thromboembolism (VTE) will also likely affect patient preferences about proceeding with hip or knee joint replacement surgery.

The intersection of the PEPPER trial and the Covid-19 pandemic provides a unique opportunity to study patient preferences regarding prioritization of high value discretionary procedures like THA and TKA, and how they are influenced by competing life or death health care issues, societal pressures, and major economic stresses. Using an expanded survey developed in conjunction with the PEPPER Patient Advisory Board (PAB), we will conduct a sub-study to assess patient concern over Covid-19 and how this affects intentions to reschedule surgery. We will thus explore the perceived value of these elective procedures, thereby informing expectations for future utilization of discretionary healthcare services. This will not interfere with the original study design and will amplify findings on patient preferences.

Specifically, we will study the cohort of patients enrolled in the PEPPER trial and scheduled for THA or TKA prior to the national pause in elective surgical procedures through deployment of an expanded survey to better understand effects of Covid on patient preferences for, and outcomes following, discretionary joint replacement surgery. We will compare patient reported mental health and surgical outcomes in pre- and post-Covid cohorts as well as VTE events in Covid patients who subsequently undergo THA/TKA. In addition, we will analyze surgical cancellation rates and rescheduling lags over the 12 months following resumption of elective procedures post-Covid at PEPPER study sites. It is anticipated that this enhancement will be accomplished in parallel with the second half of the PEPPER trial and will not otherwise delay its anticipated completion.

